8.3. Definitions of analysis sets

Analysis sets are described below and in [Figure 2](#).

8.3.1. Intent-to-treat analysis set

The Intent-to-Treat (ITT) Analysis Set will consist of all enrolled patients.

8.3.2. Safety analysis set

The Safety Analysis Set will be a subset of the ITT Analysis Set and will include all patients who receive any amount of ceftaroline fosamyl.

8.3.3. Modified intent-to-treat (MITT) analysis set

[figure not shown]
The MITT Analysis Set will include all patients who receive any amount of ceftaroline fosamyl and who meet minimal disease criteria of LOS as described in the inclusion criteria in [Section 3.1](#) (diagnosis of sepsis within 36 hours before enrolment, defined as the presence of at least 2 clinical criteria and at least 1 laboratory criterion in the presence of or as a result of suspected or proven bacterial infection that requires IV antibiotic therapy). Patients with confirmed infection with a pathogen known to be resistant to the study therapy received and patients with a confirmed fungal, parasitic, or viral pathogen as the sole cause of infection will be excluded. A list of resistant pathogens will be provided in the SAP.

8.3.4. Pharmacokinetic (PK) analysis set

The PK Analysis Set will include all patients who receive a known amount of ceftaroline fosamyl and who have had at least 1 PK sample collected (excluding those receiving blood or

blood component transfusions within 24 hours before sample collection or who are at risk from additional blood loss per the discretion of the investigator).

Figure 2 Study Analysis Sets

8.4. Outcome measures for analyses

8.4.1. Efficacy response definitions

8.4.1.1. Clinical outcome at End-of-Therapy

An assessment of clinical outcome will be made by the investigator at EOT. The clinical outcome categories are defined in [Table 4](#). A favourable clinical outcome is clinical cure. An outcome of clinical failure at EOT will be carried forward to TOC.

Table 4 Clinical outcome categories at End-of-Therapy

Outcome	Definition
Clinical Cure	Resolution of all acute signs and symptoms of LOS or improvement to such an extent that no further antibacterial therapy is required
Clinical Failure	Patients who received ≥ 48 hours of study treatment and meet any of the following: 
• Discontinuation of study therapy due to insufficient therapeutic effect, including persistence, incomplete clinical resolution, worsening in signs and symptoms of LOS, or isolation of a resistant pathogen that requires alternative nonstudy antibacterial therapy• Discontinuation of study therapy due to a study therapy-related AE and requirement for alternative nonstudy antibacterial therapy for LOS• Death in which LOS is contributory
Indeterminate	Study data are not available for evaluation of efficacy for any reason, including: 
• Death in which LOS is clearly noncontributory• Lost to follow-up• Extenuating circumstances precluding classification as a cure or failure• Diagnosis of CNS infection, osteomyelitis, endocarditis, or NEC at any time after enrolment• Received < 48 hours of study therapy

Abbreviations: AE=adverse event; CNS=central nervous system; LOS=late-onset sepsis; NEC=necrotizing enterocolitis.

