3.9.1.2. Discontinuations Due to Insufficient Therapeutic Effect

Assessments and Procedures: A patient who is prematurely discontinued from study therapy administration due to insufficient therapeutic effect should have EOT assessments conducted per [Section 4.2.5](#) and undergo subsequent safety assessments at TOC and SFU.

If a patient is discontinued from study therapy administration due to insufficient therapeutic effect and is switched to an alternative IV antibiotic, that therapy should be documented.

Clinical Outcome Assessment: A patient who is prematurely discontinued from study therapy administration (at any time after the required minimum treatment duration of 48 hours) due to insufficient therapeutic effect should be assessed as a clinical failure on the day of discontinuation (ie, EOT). Such a patient will be automatically assigned an outcome of clinical failure at all subsequent evaluation time points.

Reasons: Reasons for discontinuation from study therapy administration due to insufficient therapeutic effect may include, but are not limited to, the following:

- **Clinical Worsening:** A patient who shows signs of clinical worsening may be discontinued from study therapy administration at any time. If the investigator deems the benefit-to-risk ratio of continuing study therapy acceptable, study therapy administration for at least 48 hours is encouraged before discontinuation
- **Lack of Clinical Progress:** For a patient who is stable, yet does not show signs of improvement, the investigator is encouraged to continue study therapy administration at least 48 hours before such a patient is assessed as a clinical failure and the patient is discontinued from study therapy
- **Resistant Pathogen(s):** If an organism resistant to one or more of the components of study therapy is isolated, the investigator will determine whether the patient remains on study therapy. If clinical improvement is observed in the setting of a resistant isolate, the patient may be kept on study therapy at the discretion of the investigator. Treatment with the study therapy should be discontinued if the patient develops a concomitant bacterial infection with an organism that is not susceptible to the study therapy and requires further parenteral therapy

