8.4.1.2. Clinical outcome at Test-of-Cure

An assessment of clinical outcome will be made by the investigator at TOC. The clinical outcome categories are defined in [Table 5](#). A favourable clinical outcome is clinical cure.

Table 5 Clinical outcome categories at Test-of-Cure

Outcome	Definition
Clinical Cure	Resolution of all acute signs and symptoms of LOS or improvement to such an extent that no further antibacterial therapy is required
Clinical Failure	Patients who received ≥ 48 hours of study treatment and meet either of the following criteria: 
• Incomplete resolution or worsening of LOS signs or symptoms or development of new signs or symptoms, or isolation of a resistant pathogen requiring alternative nonstudy antibacterial therapy• Death in which LOS is contributory
Indeterminate	Study data are not available for evaluation of efficacy for any reason, including: 
• Death in which LOS is clearly noncontributory• Lost to follow-up• Extenuating circumstances precluding classification as a cure or failure• Diagnosis of CNS infection, osteomyelitis, endocarditis, or NEC at any time after enrolment• Received <48 hours of study therapy

Abbreviations: CNS=central nervous system; LOS=late-onset sepsis; NEC=necrotizing enterocolitis.

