3.2 Secondary outcome variables

3.2.1 Efficacy variables

3.2.1.1 Clinical response variable at EOT and TOC

Efficacy outcome measures will include clinical response at EOT and TOC. The clinical outcome categories at EOT are defined in [Table 4](#) below and the clinical outcome categories at TOC as defined in [Table 5](#) below. A favourable outcome is clinical cure.

Table 4 Clinical outcome categories at End-of-Therapy

Outcome	Definition
Clinical Cure	Resolution of all acute signs and symptoms of LOS or improvement to such an extent that no further antibacterial therapy is required
Clinical Failure	Subjects who received ≥ 48 hours of study treatment and meet any of the following: 
 • Discontinuation of study therapy due to insufficient therapeutic effect, including persistence, incomplete clinical resolution, worsening in signs and symptoms of LOS, or isolation of a resistant pathogen that requires alternative nonstudy antibacterial therapy • Discontinuation of study therapy due to a study therapy-related AE and requirement for alternative nonstudy antibacterial therapy for LOS • Death in which LOS is contributory
Indeterminate	Study data are not available for evaluation of efficacy for any reason, including: 
 • Death in which LOS is clearly noncontributory • Lost to follow-up • Extenuating circumstances precluding classification as a cure or failure • Diagnosis of CNS infection, osteomyelitis, endocarditis, or NEC at any time after enrolment • Received < 48 hours of study therapy

Abbreviations: AE=adverse event; CNS=central nervous system; LOS=late-onset sepsis; NEC=necrotizing enterocolitis.

Table 5 Clinical outcome categories at Test-of-Cure

Outcome	Definition
Clinical Cure	Resolution of all acute signs and symptoms of LOS or improvement to such an extent that no further antibacterial therapy is required
Clinical Failure	Subjects who received ≥ 48 hours of study treatment and meet either of the following criteria: 
• Incomplete resolution or worsening of LOS signs or symptoms or development of new signs or symptoms, or isolation of a resistant pathogen requiring alternative nonstudy antibacterial therapy• Death in which LOS is contributory

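### Clinical failure requires at least 48 hours of therapy, so early deaths from sepsis and early stops for worsening can be tabulated as indeterminate and drop out of the only clinical-response sensitivity analysis

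*Protocol*

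**What the plan says.** **Failure at End-of-Therapy (EOT).** Protocol 8.4.1.1, Table 4, opens the failure row with "Patients who received ≥ 48 hours of study treatment and meet any of the following". Three criteria follow: a stop for insufficient effect, a stop for a therapy-related adverse event (AE) with a need for non-study antibacterials, and death to which LOS contributed. The SAP version (3.2.1.1, Table 4) reads "Subjects who received ≥ 48 hours of study treatment and meet any of the following".

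**Failure at Test-of-Cure (TOC).** Protocol Table 5 uses "Patients who received ≥ 48 hours of study treatment and meet either of the following criteria", and SAP Table 5 uses "Subjects who received ≥ 48 hours of study treatment and meet either of the following criteria". LOS-contributory death is again under that condition.

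**Indeterminate.** The category is headed "Study data are not available for evaluation of efficacy for any reason, including". Its entries include "Received < 48 hours of study therapy", with no exception. The only deaths it names are those to which LOS clearly did not contribute. The text of SAP 3.2.1.1 likewise names only unrelated deaths as indeterminate.

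**Early stops.** Protocol 3.9.1.2 states: "A patient who shows signs of clinical worsening may be discontinued from study therapy administration at any time". For the outcome label, it says that a patient stopped "at any time after the required minimum treatment duration of 48 hours) due to insufficient therapeutic effect should be assessed as a clinical failure".

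**Analysis.** The MITT set takes infants given any amount of drug who meet the disease criteria (SAP 2.1.3). Indeterminates stay in the MITT denominator (SAP 3.2.1.1). Cure, failure and indeterminate are tabulated overall and by cohort, and the one clinical-response sensitivity analysis leaves indeterminates out (SAP 4.2.7.1).

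**The concern.** An infant who dies of LOS at 30 hours, or is stopped for worsening at 30 hours, has a known and unfavourable outcome. The tables place that infant in a category meant for outcomes that cannot be evaluated. The main analysis then counts every indeterminate as a non-cure, and the sensitivity analysis removes every indeterminate. Neither separates a known early LOS failure from an infant lost to follow-up.

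Three outputs could be affected: the tabulated failure proportion, the cure rate with indeterminates excluded, and microbiological response. On the last, with no culture available, clinical failure gives presumed persistence, while a clinically indeterminate infant becomes microbiologically indeterminate (SAP 3.2.1.2, Table 7 and the text after it). With about 24 infants, 8 per cohort, one relabelled infant is visible in every table.

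**Working it through.** The plan states no figure on this point: no early-event rate, no expected cure rate and no power. The check traces the labels and then applies the SAP's proportions to assumed counts.

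**1. Tracing an event before 48 hours**

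| Event before 48 h | Text giving indeterminate | Text pointing elsewhere |
|---|---|---|
| LOS-contributory death | Failure row needs 48 h; under-48-h row has no exception (both documents, Tables 4 and 5) | Indeterminate row names only deaths where LOS played no part; SAP 3.2.1.1 names only unrelated deaths |
| Stop for worsening | Same tables; Protocol 3.9.1.2 assigns failure only after 48 h | None |
| Therapy-related AE stop needing non-study antibacterials | Protocol Table 4; SAP 1.2 says so explicitly | Protocol 3.9.1.1 assigns failure with no time condition |

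No passage makes an LOS death before 48 hours a failure.

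**2. Size**

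Inputs: n = 24 in 3 cohorts of 8 (Protocol 8.2, SAP 1.3), all assumed to be in MITT. Assumed: 20 cures and 4 non-cures, of which k are early LOS deaths or worsening stops, m are indeterminate for other reasons, and f = 4 − k − m are later failures. Intervals are Jeffreys 95%, from Beta(x + 0.5, n − x + 0.5), the SAP's method.

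- Main cure rate: 20/24 = 83.3% (65.1–94.1) in every row.
- Failure as written: f/24.
- Cure with indeterminates excluded, as planned: 20/(24 − k − m).
- Added analysis: cure 20/(24 − m), failure (f + k)/(24 − m).

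| k, m | Failure as written | Cure, planned exclusion | Cure, added analysis | Failure, added analysis | Same failures on n = 24 |
|---|---|---|---|---|---|
| 0, 0 | 4/24 = 16.7% | 20/24 = 83.3% | 20/24 = 83.3% | 4/24 = 16.7% | 16.7% |
| 1, 0 | 3/24 = 12.5% | 20/23 = 87.0% (69.1–96.2) | 20/24 = 83.3% | 4/24 = 16.7% (5.9–34.9) | 16.7% |
| 2, 0 | 2/24 = 8.3% | 20/22 = 90.9% (73.9–98.1) | 20/24 = 83.3% | 4/24 = 16.7% | 16.7% |
| 1, 1 | 2/24 = 8.3% | 20/22 = 90.9% | 20/23 = 87.0% | 3/23 = 13.0% (3.8–30.9) | 3/24 = 12.5% |
| 2, 1 | 1/24 = 4.2% | 20/21 = 95.2% (79.8–99.5) | 20/23 = 87.0% | 3/23 = 13.0% | 3/24 = 12.5% |

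On the MITT denominator each such infant moves failure by 1/24 = 4.2 points overall and 1/8 = 12.5 points within a cohort. With k = 0 the failure count does not move.

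**3. Chance that it arises**

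For an assumed, independent early-event risk p per infant, the chance of at least one in 24 is 1 − (1 − p)^24: 38% at p = 2%, 71% at 5%, 92% at 10%.

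**4. The main cure rate at TOC**

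The cure row carries no 48-hour condition. SAP Table 6 turns EOT indeterminate plus TOC cure into clinical cure, whereas EOT failure is carried forward. Take k = 2, m = 0, and let one of the two be an infant stopped early for worsening and later rated cured at TOC. The Table 6 route gives 21/24 = 87.5% (70.3–96.4); had that infant been a failure at EOT, the result would be 20/24 = 83.3%. If the under-48-hour row of Table 5 is enforced at TOC, the infant stays indeterminate and the rate is 83.3% either way.

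**The case against.** The strongest reply has four parts.

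- **A minimum exposure is a legitimate design choice.** For worsening stops, Protocol 3.9.1.2 and all four outcome tables agree on it. This stands. A reader might infer that the 48-hour condition is an error throughout; the documents do not support that. What remains for these infants is that no analysis shows the result under the other definition.
- **Early LOS deaths need not be labelled indeterminate.** A reader might infer that investigators are bound to do so. The wording on unrelated deaths points the other way, and the investigator assigns the outcome (Protocol 5.1). This also stands: for deaths the texts conflict, and sites could label identical infants differently.
- **Little is at stake.** Efficacy is secondary, descriptive and untested; deaths are tabulated in the safety analysis (SAP 4.2.6.1); indeterminates are counted. It would be wrong to infer that the events are hidden. What is not reported is a failure proportion that includes them.
- **The AE-stop label is already settled for analysis.** SAP 1.2 agrees with Protocol Table 4. This stands for the derivation, but Protocol 3.9.1.1 still tells the investigator something different.

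Two opposite readings of the main cure rate are tempting. One is that it is inflated by the rule; it is not for deaths or at EOT, because indeterminates remain in the denominator. The other is that it is immune; at TOC that is not secured. Protocol 3.9.1.2 asks only for safety assessments at TOC after a stop for insufficient effect, which makes a TOC cure rating less likely but does not bar it.

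**Conclusion.** The point holds in limited form. Read literally, the tables put LOS-contributory deaths before 48 hours among the indeterminates, against other wording in the same tables and in SAP 3.2.1.1. Early worsening stops go there by a consistent rule. If either occurs, the failure proportion omits the infant, the exclusion analysis can overstate cure (by 7.6 points in the example with two early failures and no other indeterminates), and without a culture the microbiological result becomes indeterminate instead of presumed persistence.

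The size rests on assumed counts, because the documents give no early-event rate, and on the view that an early LOS death or worsening stop is informative about failure. With no early event there is no effect. With no other indeterminates, the added cure rate equals the main result (given that the under-48-hour row is enforced at TOC), and only the failure proportion gains. This is a worthwhile, inexpensive improvement to a secondary analysis, not a flaw in the primary safety objective.

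**What to change.** Keep the planned analyses and the outcome definitions. Then:

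1. In SAP 4.2.7.1 add one sensitivity analysis that counts LOS-contributory deaths and stops for insufficient therapeutic effect as failures whatever the hours of therapy, carries them forward to TOC, and excludes only the remaining indeterminates. Report cure and failure proportions, with failure also on the full MITT denominator.
2. Tabulate indeterminates by reason, splitting the under-48-hour group by cause of stopping. Show therapy-related AE stops needing non-study antibacterials as a separate line, since they are not evidence of LOS failure in the same sense.
3. State whether the under-48-hour row of Table 5 overrides SAP Table 6 at TOC.
4. Reconcile the outcome labels for early LOS death (Protocol and SAP Tables 4 and 5, and the SAP 3.2.1.1 text) and for therapy-related AE stops (Protocol 3.9.1.1 against Protocol Table 4 and SAP 1.2).

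The cost is one table, one tabulation and wording changes, with a possibly higher reported failure rate. The inputs appear to exist: cause of death (SAP 3.1.1.2), infusion date and time (Protocol 7.5), documented switch of antibiotic (Protocol 3.9.1.2) and disposition listings (SAP 4.2.1). The case report form is not among the documents, so a recorded reason for each indeterminate is not confirmed. The SAP history shows that its last versions were prepared close to database lock; if the analysis is added after lock, it should be labelled post hoc.

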1.4. Study Design

This will be an open-label, single arm study with no randomization. The study will be conducted in approximately 30 centres worldwide. At least 24 patients with LOS will be enrolled and treated within three age cohorts of 8 patients: young infants aged >28 days to <60 days; term neonates aged 7 to ≤ 28 days; and preterm neonates aged 7 to ≤ 28 days.

Study therapy consists of standard of care ampicillin plus an optional aminoglycoside of choice, with the addition of intravenous (IV) ceftaroline fosamil, and will be given to all patients. If the presence of an organism that requires treatment with ampicillin cannot be excluded, then the use of IV ampicillin for the first 48 hours is mandatory. If the results of additional microbiology, polymerase chain reaction (PCR) or other investigations indicate that ampicillin during the first 48 hours of treatment is not required, then its use is at the discretion of the investigator.

Ceftaroline fosamil will be given at a dose of 6 mg/kg IV over 60 (± 10) minutes q8h (± 1 hour).

Patient participation will require up to 49 days. The total duration of study therapy is 48 hours (minimum) to 14 days (maximum). Hospitalization is required during IV study therapy.

[figure not shown]
Baseline assessments for study eligibility will occur within 36 hours before the first dose of study therapy. The Safety Follow-up (SFU) assessments will occur 28 to 35 days after the last dose of study therapy.

Safety assessments will be done throughout the study. Between Day 2 and Day 14, 2 blood samples will be collected for PK analysis. The efficacy of ceftaroline will be evaluated based on the clinical outcome (clinical cure, clinical failure or intermediate) at end of therapy (EOT) and test-of-cure (TOC) assessment.

An external Data and Safety Monitoring Board (DSMB) will review data on a regular basis to assess the safety of all patients enrolled in this and other ongoing pediatric studies ([Section 6.5.1](#)).

The study design is described in the Study Diagram ([Figure 1](#)).

Figure 1 Study Diagram

Abbreviations: EOT = end of therapy, ICF = informed consent form, IV = intravenous, PK = pharmacokinetic, SFU = safety follow-up, TOC = test of cure

An external Data and Safety Monitoring Board (DSMB) will be established to review safety data from this study and other ongoing pediatric studies of ceftaroline fosamol on a regular basis to ensure safety of all subjects enrolled

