3.9. Discontinuation of investigational product

At any time, parent(s) or legally-acceptable representative(s) are free to discontinue the patient from treatment with IP or withdraw the patient from the study (ie, IP and assessments – see [Section 3.10.2](#)), without prejudice to further treatment. Parent(s) or legally-acceptable representative(s) who decide to discontinue a patient from treatment with IP will always be asked about the reason(s) and the presence of any adverse events. If possible, the patient will be seen and assessed by an investigator(s). Adverse events will be followed up until SFU, 28 to 35 days after the last dose of study therapy (See [Section 6](#)). Any AEs that are unresolved at the patient's last AE assessment in the study are followed up by the investigator for as long as medically indicated, but without further recording in the CRF.

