7. INVESTIGATIONAL PRODUCT AND OTHER TREATMENTS

For the purposes of this study, and per International Conference on Harmonisation (ICH) guidelines, investigational product is defined as a pharmaceutical form of an active ingredient or placebo being tested or used as a reference/comparator in a clinical trial, including a product with a marketing authorization when used or assembled (formulated or packaged) in a way different from the approved form, or when used for an unapproved indication, or when used to gain further information about an approved use (ICH E6 1.33).

For this study, the investigational product is ceftaroline fosamil.

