2.1.3 Modified Intent-to-Treat Analysis Set

The Modified Intent-to-treat (MITT) Analysis Set will include all patients who received any amount of ceftaroline fosamil and who met minimal disease criteria of LOS as described in the protocol inclusion criteria (diagnosis of sepsis within 36 hours before enrolment, defined as the presence of at least 2 clinical criteria and at least 1 laboratory criteria in the presence of or as a result of suspected or proven bacterial infection that requires IV antibiotic therapy). Patients with confirmed infection at baseline with a pathogen known to be resistant by CLSI methodologies and interpretive criteria (M100-S-28) to the study therapy received will be excluded. Patients with a confirmed fungal, parasitic, or viral pathogen as the sole cause of infection will also be excluded ([Appendix A](#)).

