4.2.6 Safety analysis

4.2.6.1 Analysis of adverse events, serious adverse events, and deaths

The number and percentage of patients with AEs occurring after the start of administration of the first dose of study therapy, or AEs that started prior to treatment and worsened on treatment, up to the SFU visit will be summarized, i.e. treatment emergent(TE) AEs. The following summaries will be presented for the Safety Analysis Set:

- Overall summary of TEAEs by category (overall and by age cohort)
- Incidence of TEAEs by system organ class (SOC) and preferred term
- Incidence of TEAEs by SOC, preferred term, and maximum intensity
- Incidence of TEAEs by SOC, preferred term, and relationship to ceftaroline
- Incidence of TEAEs of special interest by SOC and preferred term
- Incidence of non-serious TEAEs by SOC and preferred term
- Incidence of TEAEs with fatal outcome by SOC and preferred term
- Incidence of all deaths
- Incidence of Serious TEAEs by SOC and preferred term
- Incidence of TEAEs leading to discontinuation of investigational product by SOC and preferred term

All AEs occurring prior to the first intake of ceftaroline will be listed for the Safety Analysis Set.

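### An infant whose ceftaroline alone is stopped for an adverse event, and who recovers on ampicillin or an aminoglycoside, can be scored a clinical cure, and no planned analysis would show it

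*Protocol*

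**What the plan says.** **Two different treatment terms.** Protocol 1.4: "Study therapy consists of standard of care ampicillin plus an optional aminoglycoside of choice, with the addition of intravenous (IV) ceftaroline fosamil". Protocol 7: "For this study, the investigational product is ceftaroline fosamil". So study therapy is up to three drugs and the investigational product is one. SAP 4.2.5 keeps the three-drug meaning, because it tabulates study therapy exposure for each drug.

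**Objective and population.** The secondary efficacy objective (Protocol 2.2, SAP 1.1.2) names ceftaroline. SAP 2.1.3 admits to the MITT set "all patients who received any amount of ceftaroline fosamil and who met minimal disease criteria of LOS".

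**Outcome rules (Protocol Tables 4 and 5, repeated in SAP 3.2.1.1).**
- Cure at EOT is "Resolution of all acute signs and symptoms of LOS or improvement to such an extent that no further antibacterial therapy is required". It does not require that ceftaroline was continued.
- One EOT failure criterion is "Discontinuation of study therapy due to a study therapy-related AE and requirement for alternative nonstudy antibacterial therapy for LOS".
- Another begins "Discontinuation of study therapy due to insufficient therapeutic effect, including persistence, incomplete clinical resolution, worsening in signs and symptoms of LOS".
- The 48-hour minimum is counted on study treatment or study therapy.
- In the protocol, EOT and TOC are timed from the last dose or infusion of study therapy. SAP Table 2 says study drug, which it does not define.

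**Companion drugs.** After 48 hours the duration of ampicillin is left to the investigator (Protocol 7.2.2). The aminoglycoside may start or stop at any time (7.2.3). Both are exempt from the ban on other antibacterials (3.8).

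**Stopping the investigational product.** Protocol 3.9 says that parents "are free to discontinue the patient from treatment with IP". SAP 4.2.6.1 lists a table titled "Incidence of TEAEs leading to discontinuation of investigational product by SOC and preferred term". Neither says what happens to the companion drugs.

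**The concern.** No section classifies an infant who stops ceftaroline but stays on ampicillin or an aminoglycoside. The adverse-event failure criterion has two conditions: study therapy is discontinued, and a non-study antibacterial is needed. Continued companion drugs fail the second condition on any reading, and on the defined meaning of study therapy they fail the first as well.

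An infant who could not stay on ceftaroline, and who recovered on standard of care, can therefore enter the numerator of a cure rate reported against a ceftaroline objective. For that purpose the error runs upward only. It can carry into microbiology: where no specimen is available, a clinical cure becomes presumed eradication, which is a favourable response (Protocol Table 6, SAP Table 7).

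**Working it through.** The plan has no power calculation to reproduce. Its only figure is 3 cohorts × 8 = 24, which is consistent. The check is to trace a ceftaroline-only stop through the rules under two readings.

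- **Reading A:** study therapy has its defined three-drug meaning, so stopping ceftaroline alone does not discontinue it.
- **Reading B:** the heading of Protocol 3.9.1, which names the investigational product, governs. Stopping ceftaroline then discontinues study therapy, and EOT falls at that point.

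| Ceftaroline stopped, companions continued, infant recovers | Reading A | Reading B |
|---|---|---|
| Related adverse event, after 48 h | No discontinuation criterion met; EOT follows the last companion dose; cure at EOT and TOC | EOT: not cure (antibacterials still needed) and not adverse-event failure (companions are not non-study drugs), so probably indeterminate. TOC: cure if recovered and off antibacterials. SAP Table 6: indeterminate + cure = **cure** |
| Before 48 h of ceftaroline | Companion drugs complete the 48 h; cure reachable | Listed as indeterminate in Tables 4 and 5 |
| Insufficient effect, after 48 h | No discontinuation criterion met; cure reachable | Failure at EOT, carried forward (Protocol 3.9.1.2, SAP 1.2, SAP Table 6) |

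Cure at TOC is reachable on both readings in the first row, and only on Reading A in the other two.

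**Planned sensitivity analysis.** SAP 4.2.7.1 excludes indeterminates. On Reading A the infant is already a cure and stays one. On Reading B the infant leaves the EOT denominator and is still a cure at TOC.

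**Size per infant.** 1/24 = 4.2 points; 1/8 = 12.5 points. If the MITT set is smaller than 24, each infant weighs more.

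**Illustration.** The base rates and the number moved are assumptions. Intervals are Jeffreys 95%, the quantiles of Beta(x + 0.5, n − x + 0.5).

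| Infants moved from cure to non-cure | Overall, base 22/24 | One cohort, base 7/8 |
|---|---|---|
| 0 | 91.7% (75.9 to 98.2) | 87.5% (54.6 to 98.6) |
| 1 | 21/24 = 87.5% (70.3 to 96.4) | 6/8 = 75.0% (40.8 to 94.4) |
| 2 | 20/24 = 83.3% (65.1 to 94.1) | 5/8 = 62.5% (29.5 to 88.1) |

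**How often.** The documents give no rate for ceftaroline-only stops. For scale only, Protocol 1.3 reports discontinuation due to adverse events in 35/1300 = 2.7% of ceftaroline patients in pooled Phase III trials. That is a different population, and the figure is not specific to stopping ceftaroline while other drugs continue. At that rate the expected number in 24 is 24 × 35/1300 = 0.65, and P(at least one) = 1 − (1 − 35/1300)^24 = 48%. Over an assumed range of 1% to 10%, P(at least one) runs from 21% to 92%.

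**The case against.** The strongest reply has four parts.

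1. **Poor response is addressed.** A reader might infer that an infant taken off ceftaroline for poor response also becomes a cure. The documents do not support that as a settled result. Protocol 3.9.1.2 sits under a heading that names the investigational product and assigns failure after 48 hours at EOT and all later visits; SAP 1.2 repeats the rule. A reader might also infer that every failure after a stop needs a non-study drug. That condition is explicit for the whole criterion only in the adverse-event bullet. In the insufficient-effect bullet it most naturally attaches to resistant pathogens. This part stands.
2. **The terms are mixed throughout.** The Safety set is defined by receipt of ceftaroline in Protocol 8.3.2 and described by receipt of study therapy in 8.5.2. Protocol 3.9 contrasts stopping the product with leaving the study, not with continuing companion drugs. This shows that the text is ambiguous, but it does not remove the adverse-event path, which reaches cure on both readings.
3. **The regimen is what is being evaluated.** Protocol 1.1 and SAP 1.2 describe ceftaroline with ampicillin and an optional aminoglycoside. In a single-arm study even a full course cannot separate ceftaroline from its companions, and efficacy is secondary and descriptive. This stands as a reason to leave the outcome tables alone and to label the rate as that of the regimen.
4. **The data can be traced.** Per-drug exposure is tabulated, and ceftaroline administration and outcomes are listed by patient. With 24 infants a careful reader could find such cases. But no planned table links the two, and the cure rate and its interval are reported without that link.

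**Conclusion.** The point holds for adverse-event stops. A ceftaroline-only stop for a related adverse event, followed by recovery on ampicillin or an aminoglycoside, meets no adverse-event failure criterion and can be a clinical cure at TOC on either reading. A stop before 48 hours can also reach cure if the minimum is counted on the three-drug therapy. For insufficient effect the text is ambiguous, and Protocol 1.4, 3.9.1, 3.9.1.2, 7 and 8.4.1.1 and SAP 1.2 must be reconciled.

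Each affected infant is worth 4.2 points of 24 or 12.5 points of a cohort of 8. The number of such infants is not in the documents and may be zero. No test, power or sample-size figure changes.

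Two further inferences go too far. The first is that a single infusion followed by companion drugs is an endorsed ceftaroline cure: that is a constructed extreme, outcome is the investigator's assessment, and extenuating circumstances allow indeterminate. The second is that a switch prompted by culture results hides a failure: it is neither an adverse event nor poor response, and scoring it as failure would bias the rate downward.

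**What to change.** Leave Tables 4 and 5 as they are and amend the SAP before database lock:

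- **SAP 4.2.7.1:** add one sensitivity analysis of clinical cure at EOT and TOC in the MITT set, with the Jeffreys interval. Count as non-cure, and keep in the denominator, any infant whose ceftaroline fosamil stopped before 48 hours, or for an adverse event or insufficient effect, while ampicillin, an aminoglycoside or another antibacterial for LOS continued.
- **De-escalation prompted by culture results:** report it as a separate count, not as failure. State in advance which rule applies if it falls before 48 hours.
- **SAP Table 2:** state which drug's last dose study drug means for the EOT and TOC windows.
- **Labelling:** describe the main cure rate as that of the ceftaroline-containing regimen.

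The cost is one more SAP version and one table. Infusion dates and times are recorded (Protocol 7.5), per-drug exposure is already derived (SAP 4.2.5), and adverse events leading to a product stop are already tabulated (SAP 4.2.6.1). The documents do not show whether a reason other than an adverse event is recorded for ceftaroline separately, so check this against the CRF. The sensitivity cure rate may be slightly lower than the main one. Patient care does not change.
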